6.2. General Considerations

Statistical analysis of this study will be the responsibility of Eli Lilly. Analyses will be conducted using SAS 9.2 (or later).

Efficacy analyses will be conducted on the full analysis set (FAS), unless otherwise stated. The FAS includes all data from all randomized patients receiving at least 1 dose of the study drug according to the treatment the patients were assigned. When mean change from baseline to endpoint is assessed, data will be included in the analysis only if there is a baseline and a corresponding postbaseline measure.

Safety analyses will be conducted on the safety analysis set. This set includes all randomized patients who received at least 1 dose of study drug. Safety analyses will be based on the treatment the patients actually received.

Analyses based on the per-protocol set (PPS) will be performed to examine the robustness of the primary efficacy analysis. The PPS will be defined as a subset of patients in FAS who did not have major protocol deviations.

All tests of hypotheses will be considered statistically significant if the 2-sided p-value is <0.05 , unless otherwise stated. No adjustments for multiple comparisons will be made.

Any change to the data analysis methods described in the protocol will require an amendment ONLY if it changes a principal feature of the protocol. Any other change to the data analysis methods described in the protocol, and the justification for making the change, will be described in the SAP and clinical study report. Additional exploratory analyses of the data will be conducted as deemed appropriate.

Baseline value for a variable will be defined as the last non-missing value for this variable prior to or at randomization visit (Visit 2), unless otherwise specified.

The endpoint value for an efficacy variable is defined as the last non-missing post baseline value prior to or at Visit 6 (Week 12), unless otherwise stated.

The endpoint value for a safety variable is defined as the last non-missing post baseline value prior to or at Visit 7 (Week 13), unless otherwise stated.

In general, descriptive summary statistics will include:

- for categorical variables: number and percentage (with the percentage excluding the number missing in the denominator)
- for continuous variables: number, mean, median, standard deviation, minimum, and maximum.

Percentages will be reported to one decimal place; mean and median to one decimal place more than the raw data; standard deviation and standard error to two decimal places more than the raw data; minimum and maximum the same as the raw data.

Only one data lock is planned for this study, when all patients have completed all study procedures. No interim analyses are planned.

6.3. Handling of Dropouts or Missing Data

When the imputation for the missing data will be needed, the baseline observation carried forward (BOCF) and last observation carried forward (LOCF) methods will be used for the primary efficacy endpoint. And the LOCF method will be used for the others. The imputation will not be conducted unless otherwise stated.

6.3.1. Baseline Observation Carried Forward

A BOCF analysis will be performed on the primary variable. For patients discontinuing the study drug due to an adverse event (AE), death or lack of efficacy, the baseline observation will be carried forward to the corresponding primary endpoint evaluation. Otherwise, the last non-missing post baseline observation will be carried forward to the corresponding primary endpoint

for evaluation. Randomized patients without at least 1 post baseline observation will not be included for evaluation with the exception of patients discontinuing study treatment due to an AE, death or lack of efficacy.

6.3.2. Last Observation Carried Forward

A LOCF analysis will be performed on the primary and the other variables unless otherwise stated. Regardless the patients completed the study or discontinued the study treatment due to any reason, the last non-missing post baseline observation will be carried forward to the corresponding endpoint for evaluation. Randomized patients without at least one post-baseline observation will not be included for evaluation.

6.4. Patient Disposition

Reasons for study and study treatment discontinuation will be summarized by treatment group and period including treatment period, tapering period and follow-up period. The significance of the differences in percentages of each reason for discontinuation between the duloxetine and pregabalin treatments groups will be assessed using the Fisher's exact test.

By-patient listing of patient discontinuation of each study period will be presented for all randomized patients.

6.5. Important Protocol Deviations

The number and percentage of patients with important protocol deviations will be summarized and listed for all randomized patients.

6.6. Patient Characteristics

Patient demographics (age, gender, race, height, and weight) and patient disease characteristics (types of diabetic mellitus, duration of diabetes, duration of diabetic neuropathy, duration of diabetic neuropathy pain, alcohol consumption, and baseline HbA1c) will be summarized for the FAS population, as well as the baseline pain severity measurements (weekly mean of 24-hour average pain score, weekly mean of night pain score, weekly mean of 24-hour worst pain score, and BPI-SF score). In addition, baseline assessment for mood and general illness (PGI-Severity, BDI-II, NPSI, and CGI-Severity) will be summarized for the FAS population. For each of the measures mentioned above, the overall treatment group differences will be examined using the Analysis of Variance (ANOVA) model, with the terms of treatment for the continuous variables, and the Fisher's exact test for the categorical variables.

6.7. Historical Illness and Pre-existing Conditions

Significant historical illnesses and pre-existing conditions will be coded from the actual term using the Medical Dictionary for Regulatory Activities (MedDRA) dictionary.

Pre-existing conditions are defined as those conditions recorded on the Pre-existing Conditions and AEs electronic case report forms (eCRF) page with a start date prior to the date of informed consent, and no end date (i.e. the event is ongoing) or an end date after the date of informed consent. If a pre-existing condition worsens in severity on or after the date of informed consent,

it will be considered an AE from the date of worsening onwards. Patients will only be counted once, regardless of how many conditions are included under the same System Organ Class (SOC) and Preferred Term.

The number and percentage of patients with significant historical illness will be summarized by treatment group by MedDRA Preferred Term based on the FAS population. In addition, the number and percentage of patients with pre-existing conditions will be summarized similarly.

By-patient listings of historical illnesses and pre-existing conditions will be provided.

6.8. Concomitant Therapy

Medications will be coded according to the World Health Organization (WHO) dictionary. Previous medications are those medications that started and stopped before the first day of the study treatment. Concomitant medications are those medications used during the study.

The number and percentage of patients with previous medications will be summarized by Anatomical Therapeutic Chemical (ATC) class (level 4) and WhoDrug preferred term and by treatment group.

The number and percentage of patients receiving concomitant medications other than analgesics and the number and percentage of patients receiving analgesics concomitant medications will be summarized by ATC class (level 4) and WhoDrug preferred term and by treatment group respectively. The significance of differences between the treatment groups will be assessed via the Fisher's exact test.

By-patient listings of previous medications and concomitant medications will be provided.

6.9. Treatment/Diary Compliance

Treatment compliance will be calculated based on the number of capsules taken (calculated from the number of capsules dispensed and returned) and the number of days between visits as a percentage of the number of capsules prescribed for a period of that length. Patients will be considered compliant for a particular visit if 80% to 120% of the prescribed capsules were taken. Overall treatment compliance will be defined as being compliant at all non-missing visits. The numbers and percentages of patients with treatment compliance or non-compliance with compliance level (Never (0%), Significantly less than prescribed (<80%), and More frequently than prescribed (>120%)) will be summarized by visits and overall by treatment group, and the treatment group differences will be assessed via the Fisher's exact test.

A patient will be considered to be compliant with the diary at a certain visit if the patient completed at least 80% of the diaries over the total days since the last visit. A patient will be considered to be compliant overall with the diary if the patient is compliant with the diary at each visit in the study period from Visit 2 through Visit 6. Diary compliance percentages will be summarized descriptively for all visits by treatment group. The numbers and percentages of patients with diary compliance will be summarized by visits and overall by treatment group, and the treatment group differences will be assessed via the Fisher's exact test.

By-patient listings of treatment compliance and diary compliance will be provided.

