## 9.5.1. Special Treatment Considerations

To help minimize the risk of discontinuation reactions, study drug doses will be tapered for selected dose regimens during Period 3 (Visit 6 [Week 12] to Visit 7 [Week 13]) before study drugs are discontinued. The following tapering regimes will apply to patients whose final study drug dose, during Period 2, were duloxetine 40/60 mg/day or pregabalin 300/450/600 mg/day.

If a patient discontinues during the first week of double-blind treatment, his/her medication should be discontinued abruptly.

If a patient discontinues during or after the second week of double-blind treatment, his/her medication should be tapered over 7 days as follows, depending on the dosage when they discontinue.

- Duloxetine final dose of 40 mg/day
  - $\circ$  20 mg/day for 7 days
- Duloxetine final dose of 60 mg/day
  - $\circ$  40 mg/day for the first 3 days
  - $\circ$  20 mg/day for the last 4 days
- Pregabalin final dose of 300 mg/day
  - $\circ$  150 mg/day for 7 days
- Pregabalin final dose of 450 mg/day
  - $\circ \quad$  300 mg/day for the first 3 days
  - $\circ$  150 mg/day for the last 4 days
- Pregabalin final dose of 600 mg/day
  - 300 mg/day for the first 3 days
  - $\circ$  150 mg/day for the last 4 days

A patient may be discontinued from the study without being tapered off his/her medication if the patient refuses to be tapered, or in the case of a SAE, for patient safety or ethical reasons.

Patients who are discontinuing from the study must attend the study site for an early discontinuation (ED) visit and to receive study drug for dose tapering (if applicable). These patients must attend the study site for a follow-up visit (Visit 301) 1 week after the end of study drug tapering (Visit 7). For patients who discontinue the study drug without tapering, they must still attend the study site for an ED visit and a follow-up visit (Visit 301).

Restricted medications are summarized in Protocol Addendum F1J-JE-HMHA (1413N0841).

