## 9.9. Treatment/Diary Compliance

Patient compliance with study medication will be assessed at each visit. Compliance will be assessed by direct questioning and counting returned tablets. Deviation(s) from the prescribed dosage regimen should be recorded in the eCRF.

Diary completion will directly affect primary efficacy data collection; thus, the status of compliance with diary completion will be assessed at each visit from Visit 2 to Visit 6. A patient will be considered to be compliant with the diary at each visit if he/she has completed at least 80% of the diaries over the total days since the last visit.

Compliance for each visit interval is defined as taking between 80% and 120% of the study drug dosage prescribed for that interval. The first time a patient is noncompliant, the patient will be counseled on the importance of taking the prescribed amount of study drug(s). The second time (either consecutive or nonconsecutive) that a patient is noncompliant, Lilly or its representative will be notified.

Patients who are significantly noncompliant may be discontinued from the study. A patient will be considered significantly noncompliant if he/she is judged by the investigator to have intentionally or repeatedly taken more than the prescribed amount of medication.

Patients should be instructed to return all study drug packaging and unused study drugs and supplies to the study site at each visit. The study site will keep a record of all study drugs dispensed to and returned by the patients throughout the study. The study site will return all unused study dugs to Lilly or its designee. The investigator (or designee) at each investigational site will be responsible for keeping a drug accountability log. A drug reconciliation will be performed as appropriate, for example, throughout, and at the end of the study.

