# Attachment 1. Protocol HMHA Study Schedule

#### Study Schedule, Protocol F1J-JE-HMHA (1413N0841)

Perform procedure as indicated.

	Perio	od 1	Period 2 Treatment			Period 3	Period 4		
Visit	Visit 1	Visit 2	Visit 3	Visit A	Visit 5	Visit 6		Visit 7	Follow up Visit 301
VISIC	Visit I Weeks	v 1811 2	v ISIT J	v 1510 4	v isit 5	VISIC U		Wook 12/	Week 14/
Wook	-2 to -1	Week 0	Wook 2	Wook 1	Wook 8	Wook 12	FD	discontinuationa	discontinuationb
VV CCK	-2 to -1	WEEKU	WCCK 2	WCCK 4	WEEK O	WCCK 12	ЕЛ	uiscontinuation	uiscontinuation~
Day	-14 to -7	Day 0	Day 14	Day 28	Day 56	Day 84	-	-	-
Allowable range	_	-	±7 days	±7 days	±7 davs	+ 7 days	+ 3 days c	+ 3 days	+ 3 davs
Patient characteristics/ diagnosis			• •••••) ~				unjo		
Consent obtainment	Y								
Patient characteristics	Y								
Diagnosis of diabetic neuropathy	Y								
Past history/ complications	Y	Y							
Treatments								•	
Drug allocation		Y							
Prescription of the investigational		Y	Y	Y	Y	Y	Y		
drugs									
Recovery of the investigational drugs/			Y	Y	Y	Y	Y	Y	
confirmation of remaining drugs									
Concomitant (previous)	Y	Y	Y	Y	Y	Y	Y	Y	
drugs/treatments				l					
Efficacy evaluation	1	1	1	1	1	1	1	[	[
24 hour every go noin									
Worst pain	<						$\rightarrow$		
Night pain									
PGI-S		Y							
PGI-I			Y	Y	Y	Y	Y		
BPI-SF		Y	Y	Y	Y	Y	Y		
BDI-II		Y		Y	Y	Y	Y		
MINI		Y							
CGI-S		Y							
CGI-I			Y	Y	Y	Y	Y		

	Perio	od 1			Period 2			Period 3	Period 4
	Scree	ning		r.	Freatment			Tapering	Follow up
Visit	Visit 1	Visit 2	Visit 3	Visit 4	Visit 5	Visit 6		Visit 7	Visit 301
	Weeks							Week 13/	Week 14/
Week	-2 to -1	Week 0	Week 2	Week 4	Week 8	Week 12	ED	discontinuation a	discontinuation b
	Day								
Day	-14 to -7	Day 0	Day 14	Day 28	Day 56	Day 84	-	-	-
							+ 3		
Allowable range	-	-	±7 days	±7 days	± 7 days	+ 7 days	daysc	+ 3 days	+ 3 days
NPSI		Y				Y	Y		
EQ-5D		Y				Y	Y		
Safety evaluation					•	•	•		
Adverse events	$\leftarrow$			-					$\longrightarrow$
Hematology/clinical chemistry	Y			Y	Y	Ye	Yf	Y	
HbA1cd	Y			Y	Y	Y	Yf	Y	
Urinalysis	Y			Y	Y		Y	Y	
CrCL	Y								
Duran un autorit	Y	The test i	s performed	l, as appropi	riate, when				
Pregnancy test		the possibility of pregnancy is suspected.							
Sitting blood pressure/heart rate	Y	Y	Y	Y	Y	Y	Y	Y	
Electrocardiographyg	Y						Y	Y	
C-SSRS	Y	Y	Y	Y	Y	Y	Y	Y	
Body weight		Y		Y		Y	Y	Y	
Fall Ouestionnaire	1	Y	Y	Y	Y	Y	Y	Y	

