Abbreviations: BDI-II = Beck Depression Inventory-II; BPI-SF = Brief Pain Inventory-Short Form; CGI-I = Clinical Global Impression of Improvement; CGI-S = Clinical Global Impression of Severity; CrCL = Creatinine Clearance; C-SSRS = Columbia Suicide Severity Rating Scale; EQ-5D = EuroQol

5 Dimension; ED = Early Discontinuation; MINI = Mini-International Neuropsychiatric Interview; NPSI = Neuropathic Pain Syndrome Inventory;

NRS = numeric rating scale; PGI-I = Patient Global Impression of Improvement; PGI-S = Patient Global Impression of Severity.

- a Visit 7 occurs 7 days (+3) after Visit 6 or early discontinuation visit. Patients who discontinue the study drug without tapering do not require this visit. (See Section 9.5.1.)
- b Visit 301 occurs 7 days (+3) after Visit 7 or ED Visit without tapering.
- c ED is considered as the same day of the last administration. Variables for ED visit will be evaluated within 3 days after the last administration.
- d When there are multiple HbA1c values measured at different institutes, the value measured at the same institute at Visit 1 is used for this eligibility judgment. If both values measured by the central laboratory are available, the most recent data should be used for this eligibility judgment.
- e Glucose (fasting), Clinical chemistry only.
- f This will be applied to patients who discontinue the study without tapering.
- g ECG will be evaluated for patients who have a risk of cardiovascular events based on the investigator's decision.

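### The SAP's treatment-compliance formula and Protocol 9.9 diverge at Visit 7, so a permitted late taper visit can score a fully adherent patient below 80%

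*SAP*

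**What the plan says.** **The formula.** SAP 6.9 and Protocol 12.2.5 take the capsules used (dispensed minus returned) and "the number of days between visits as a percentage of the number of capsules prescribed for a period of that length". SAP 6.9 then sets the band: "Patients will be considered compliant for a particular visit if 80% to 120% of the prescribed capsules were taken". The overall rule follows: "Overall treatment compliance will be defined as being compliant at all non-missing visits".

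**The other definition.** Protocol 9.9 uses the same 80% to 120% band, but relative to the dosage prescribed for the visit interval. It does not scale to the interval's length.

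**Which visits count.** Protocol 9.9 states: "Patient compliance with study medication will be assessed at each visit". The Attachment 1 row that begins "Recovery of the investigational drugs" is marked at Visit 7, so capsules are counted there. SAP 6.9 ends the diary measure at Visit 6 ("compliant with the diary at each visit in the study period from Visit 2 through Visit 6") but sets no such end for treatment compliance.

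**The taper and its visit.** For completers, Protocol 7.1 and Table HMHA.1 give a one-week taper, split 3 + 4 days after a dose increase. For patients who stop from the second week on, Protocol 9.5.1 says "his/her medication should be tapered over 7 days as follows". Attachment 1, footnote a, sets the window: "Visit 7 occurs 7 days (+3) after Visit 6 or early discontinuation visit".

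**The concern.** During the 12-week treatment period the patient keeps dosing until the next visit. Scaling the denominator to the days between visits therefore gives the number of capsules that should have been taken. In the taper interval dosing stops after 7 days, yet the interval may last up to 10. If the denominator grows with the interval, it counts capsules that nobody was told to take.

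Overall compliance needs every non-missing visit inside the band, so one shortfall at Visit 7 is enough to fail a patient. What is at stake is the overall compliance percentage, the count in the below-80% category, and the Fisher's exact test between arms. These should describe adherence, not the date of a visit held after dosing ended.

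**Working it through.** The documents state no compliance percentage, so there is no planned figure to reproduce. The check applies the two rules to a patient who takes every taper capsule and nothing more.

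**Inputs**
- Capsules per day in the taper (Table HMHA.2): without a dose increase, 4 morning + 3 evening = 7 on all 7 days. After any increase, 3 + 1 = 4 for 3 days, then 4 + 3 = 7 for 4 days. The table is partly garbled in the extracted text, but these counts match its rows for the same doses in weeks 0 to 1 and weeks 1 to 4.
- Taper totals: 7 × 7 = **49**; (4 × 3) + (7 × 4) = 12 + 28 = **40**.
- Days from Visit 6 or the early discontinuation visit to Visit 7: 7, 8, 9 or 10 (Attachment 1, footnote a).
- Band: 80% to 120% (SAP 6.9; Protocol 9.9).

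**Rule A, SAP 6.9 read literally.** Score = capsules taken / capsules for a period as long as the interval. After a dose increase the daily rate is not constant and the SAP does not say how to extend it, so both the mean daily rate (40/7) and the last-day rate (7) are shown.

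| Visit 7 on day | No increase | After increase, mean rate | After increase, last-day rate |
|---|---|---|---|
| 7 | 49/49 = 100.0% | 100.0% | 40/40 = 100.0% |
| 8 | 49/56 = 87.5% | 7/8 = 87.5% | 40/47 = 85.1% |
| 9 | 49/63 = 77.8% | 7/9 = 77.8% | 40/54 = 74.1% |
| 10 | 49/70 = 70.0% | 7/10 = 70.0% | 40/61 = 65.6% |

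At a constant or mean rate the score is 7/d, which drops below 80% once d exceeds 7/0.8 = 8.75 days. With this day count, a visit 1 day late passes and a visit 2 or 3 days late fails, for every taper pattern.

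**Rule B, Protocol 9.9.** Score = capsules taken / capsules prescribed in the interval = 49/49 or 40/40 = 100% on any day from 7 to 10.

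**Sensitivity to day counting (mean rate).** If both visit days are left out, the interval is d − 1 days: day 9 gives 7/8 = 87.5% and day 10 gives 7/9 = 77.8%, so only day 10 falls below 80%. If both are counted, the interval is d + 1 days: day 8 gives 7/9 = 77.8%, so days 8 to 10 all fall below 80%. Neither document fixes the convention.

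**The case against.** The strongest reply is that the Protocol already answers the question. Protocol 9.9 defines compliance against what was prescribed for the interval, and between Visit 6 and Visit 7 that is the 7-day taper alone. The SAP wording can also be read as the capsules prescribed over those days, with none on days 8 to 10. On that reading the score is 100% and nothing is wrong. This stands in part: it rules out calling misclassification certain. It does not remove the problem, because SAP 6.9 and Protocol 12.2.5 tie the denominator to the interval's length, give no taper rule, and leave the choice to the programmer.

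Protocol 9.2 also provides additional capsules for permitted deviations in visit timing. That bears on what a late patient might have in hand, but no section extends the taper beyond 7 days.

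A third reply is that results are summarised by visit as well as overall, with by-patient listings, so a dip at Visit 7 would be visible. That is true of the by-visit rows; the overall figure and its test would still carry the dip.

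Finally, the consequences are small. A reader might infer a bias between arms, or an effect on the non-inferiority result. The documents support neither. Under the double-dummy design both arms have the same capsule counts for each regimen and the same visit window. Nothing links this percentage to the primary model, and the per-protocol set is defined by major protocol deviations without reference to it.

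**Conclusion.** The point holds as a conflict between two stated rules that matters only at Visit 7. Under the literal SAP formula, a patient who took every taper capsule scores about 87.5%, 77.8% or 70.0% on day 8, 9 or 10. Under Protocol 9.9 the same patient scores 100%. A permitted late visit can therefore make an adherent patient non-compliant at Visit 7 and so overall.

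This rests on three assumptions: the denominator is extended to the visit date, the interval is counted as the simple difference in days, and Visit 7 enters the overall rule, which SAP 6.9 does not exclude. Three stronger readings go too far:
- That every patient seen 2 or 3 days late is misclassified. This depends on the day count; with both visit days excluded, only day 10 falls below 80%.
- That scores fall as low as 65.6%. This needs the last-day rate, which is not written anywhere.
- That overall compliance drops by some particular number of points. If a share p of all patients in the summary fell below 80% for this reason alone, the drop would be p, but the documents give no late-attendance rate.

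What remains is understated adherence and added noise in one descriptive table and its Fisher's exact test. It is a minor point.

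**What to change.** Add one sentence to SAP 6.9, in line with Protocol 9.9: for the interval ending at Visit 7, the denominator is the number of capsules prescribed for the 7-day taper (49, or 40 after a dose increase), whatever the visit date. A fully adherent patient then scores 100% on any day from 7 to 10.

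The cost is that sentence and a small programming change. It needs no new data and does not alter the taper. Because Protocol 12.2.5 carries the same formula as the SAP, the departure and its reason should also be recorded in the clinical study report, as SAP 6.2 provides for changes that do not affect a principal feature.

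Reporting overall compliance for the 12-week treatment period separately from the taper is optional. The taper is prescribed double-blind drug, so keeping it in the overall figure is legitimate once its denominator is right.
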